In sum, by demonstrating the ability of bupropion vs escitalopram to increase FC in reward circuitry and reduce motivational deficits in MD patients with increased inflammation and anhedonia, this pilot study will not only help establish a mechanism of action for bupropion but will also help provide an important foundation for preferentially using bupropion (and other medications that target DA) in patients with increased inflammatory biomarkers such as CRP and anhedonia, thus supporting precision medicine using available antidepressants.

PI: [name] Sponsor: NIMH

5. Study design and methods:

Study Population: Fifty male and female subjects ages 25-55 will be randomized to obtain 40 with complete data (20% projected attrition). Subjects will be recruited from a community sample of MD patients through social media.

Participant Selection

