Criteria for Study Discontinuation ("Stopping Rules"):

Individual:

To reduce the risks associated with active treatment, all subjects will be monitored carefully for the development of adverse events as well as worsening of their condition. Between signing consent and completing the screening assessment, a period of no more than 2 weeks will pass until baseline. Subjects will be closely evaluated throughout the study both virtually and during study visits for worsening of psychiatric symptoms. Moreover, all patients are provided 24/7 access to study personnel in the event of an emergency. Subjects will be discontinued at any point for any of the following: 1) the development of significant suicidal ideation, plan or intent as determined by spontaneous subject report or as determined by CSSRS,⁴¹ 2) the development of psychotic or catatonic symptoms, 3) a 25% increase from baseline of HAM-D-17 score, 4) missing more than 2 consecutive doses of medication more than once during the study, and 5) positive pregnancy test. Subjects requiring discontinuation will be referred for further evaluation and treatment by one of the study psychiatrists.

1) If more than two individuals experience a reportable serious adverse event related to study procedures within a six-month period, the study will be stopped and reviewed by the DSMB.

Neuropsychiatric Assessments

Structured Clinical Interview for DSM-V Axis I Disorders (SCID-V) is a semi-structured clinical interview that provides a wide range of DSM-V diagnoses. ⁴² All patients will be evaluated by a modified SCID as part of the screening process. In addition to providing information for inclusion/exclusion purposes, the SCID will provide data about psychiatric predictors of treatment response, including number of past major depressive episodes, length of the current episode and presence of co-morbid anxiety disorders and/or dysthymia.

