Aim 1: To determine whether bupropion (vs escitalopram) will increase FC in reward circuitry. Hypothesis 1: Bupropion vs escitalopram will increase VS-vmPFC FC in depressed patients with high CRP and anhedonia at baseline. Primary Endpoint: Targeted VS-vmPFC FC at 8 weeks. Predictors: group (bupropion vs escitalopram), time (baseline, 8 weeks), and group x time interactions. Covariates: Primary: Age, sex, BMI, race. Additional covariates: Number of depressive episodes, length of current depressive episode (in months), treatment trials (ATRQ), age of onset, and family history of depression (ves/no), weeks on targeted dose of medication, Analysis Plan: Subjects will be randomized to two different treatment groups and scanned across two visits. Consequently, a factorial mixed-effects models for repeated measures (MMRM) will be employed with group, time and group x time interaction on targeted VS-vmPFC FC as fixed effects and each subject's baseline (identity) as random effects. Linear and multi-level mixed effects will be evaluated using both unstructured and autoregressive covariance structures and restricted maximum likelihood estimation and will be used to predict random effects (slope and intercept) in addition to fixed effects, optimized using Bayesian Information Criteria (BIC). Primary and additional covariates will be entered in all models as random variables after testing for significant associations. Given the inherently noisy nature of the covariates, model tuning to optimize the balance between explanatory (r²) and noise variables (root mean square error) will be undertaken to select the most parsimonious models using BIC. The MMRM will also be augmented using Elastic net generalized regression models using group||time nesting approaches. Models will be selected using model comparison metrics. All analyses will be conducted in accordance with published guidelines.⁷⁶ Exploratory analysis: A similar analysis as indicated above will be conducted on fMRI scans conducted at 4 weeks. The 4-week scan will be conducted based on the rapid effects seen with dopamine agonists in our preliminary studies with L-dopa (data not shown).

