Risks and side effects of these medications vary in type and severity depending on the drug, but include gastrointestinal distress, headaches, sexual dysfunction, anxiety, high blood pressure, induction of mania, suicidal ideation, seizures and potential lethality in overdose. To reduce the risks associated with active treatment, all subjects will be monitored carefully for the development of adverse events as well as worsening of their condition. Specific indications for discontinuation between screening and baseline will include any of the following at the Pl's discretion: 1) the development of significant suicidal ideation, plan or intent as determined by spontaneous subject report or as determined by CSSRS, 41 2) the development of psychotic, manic/hypomanic or catatonic symptoms, 3) a 25% increase from baseline of HAM-D-17-17 score. 4) missing more than 2 consecutive doses of medication more than once during the study, and 5) a positive pregnancy test at any point during the study. Other criteria for discontinuation between screening and the baseline visit include: hospitalization for any reason or a clinical judgment that a subject is an imminent threat to self or others. Upon discontinuation, subjects will be immediately evaluated by a study psychiatrist and determination of the appropriate level of care, including emergency hospitalization, will be determined. Subjects with non-urgent symptoms but who disqualify for further participation and who are in active treatment will be referred to their primary psychiatric physician. Participants will be required to identify a primary care or psychiatric physician at study entry to ensure seamless psychiatric care following study completion. All depressed subjects without a current psychiatrist will be offered an appropriate referral. The unblinded study physician may break the treatment blind following study completion or early termination from study participation. Participants with adequate treatment response at study completion may receive a 4 week supply of identified study medication. At the end of the study, or in the event of Early Termination, patients not achieving a 50% or greater treatment response as measured by the Ham-D-17 total score, they will be given a prescription to continue medication for 1 tablet daily for 7 days before stopping the medication (if on 2 pills of study medication at the end of the study). An individualized plan will be crafted for each subject to ensure psychiatric back-up should emergency psychiatric care be required after hours or on weekends. During the treatment study itself, subjects will be discontinued at any point for any of the following: 1) the development of significant suicidal ideation, plan or intent as determined by spontaneous subject report or as determined by the Columbia Suicide Severity Rating Scale, 2) the development of psychotic or catatonic symptoms, 3) a 25% increase from baseline of HAM-D-17 score, 4) missing more than 2 consecutive doses of medication more than once during the study and 5) positive pregnancy test at any point during the study. Subjects requiring discontinuation will be referred for further evaluation and treatment by one of the study psychiatrists as described above.

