Subjects will be closely evaluated throughout the study for worsening of psychiatric symptoms. Subjects will be discontinued at any point for any of the following at the Pl's discretion: 1) the development of significant suicidal ideation, plan or intent as determined by spontaneous subject report or as determined by CSSRS,⁴¹ 2) the development of psychotic, manic/hypomanic or catatonic symptoms, 3) a 25% increase from baseline of HAM-D-17 score, 4) missing more than 2 doses of medication more than once during the study, and 5 a positive pregnancy test at any time during the study. Subjects requiring discontinuation will be referred for further evaluation and treatment by one of the study psychiatrists or clinicians.

Compensation to Participants:

Participants will receive up to \$400-\$1500 for participation of the study. Participants will be compensated using ClinCard. The ClinCard is a web based, reloadable, debit card that automates reimbursements for clinical research participants. An additional \$25 will be provided to cover travel expenses for participants that travel equal to or greater than 50 miles to Atlanta. Candidates deemed ineligible by virtual evaluation(s)prior to the first in person office visit will not be compensated.

Visit	Total Amount	Amount put on Clincard immediately after visit	Amount put on Clincard at the end of study participation
Intake (Virtual when possible)	No Payment	No Payment	No Payment
(Visit Total)			
Visit 1 (Screen A)			
Screening lab work, UDS, Preg Test, AEs, Concomitant Meds	\$50*	\$50*	
(Visit Total)	\$50		
Visit 2 (Screen B & Baseline A)			
Physical Exam, Rapid CRP, Vitals, research bloods, urine toxicology and pregnancy test, self-report surveys	\$50	\$50	
Computer Task (depending on choice made on the computer)	\$5-\$10	\$5-\$10	
(Visit Total)	\$55-\$60		
Visit 3 (Baseline B)			
Medical and psychiatric assessments, vitals, self-report surveys and medication check and randomization and medication administration	\$50	\$50	
Computer Task (depending on choice made on the computer)	\$5-\$30	\$5-\$30	
Complete Scan	\$200		\$200
Incomplete Scan	\$25**	\$25**	
(Visit Total)	\$80-\$280		
Visit 4 (Week 2)			
Medical and psychiatric assessments, self-report surveys and medication check	\$50	\$50	

PI: [name] Sponsor: NIMH

Sponsor: NIMH			
Computer Task (depending on choice	\$5-\$10	\$5-\$10	
made on the computer) (Visit Total)	\$55-\$60		
Visit 5 (Week 4)			
Medical and psychiatric assessments,	\$50	\$50	

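### Patients who worsen on HAM-D-17 or repeatedly miss doses leave the study, not only the drug, so they drop out of the week-8 FC contrast for reasons that may depend on treatment

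*Combined protocol and SAP*

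**What the plan says.** Section 5, under Criteria for Study Discontinuation, says that subjects are discontinued at any point for listed events, including "a 25% increase from baseline of HAM-D-17 score, 4) missing more than 2 consecutive doses of medication more than once during the study". What follows is clinical referral: "Subjects requiring discontinuation will be referred for further evaluation and treatment by one of the study psychiatrists". Section 13 (medication risks) repeats the rule for the treatment period. It also says that the unblinded study physician "may break the treatment blind following study completion or early termination from study participation".

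Table 1 has no early-termination visit or scan. Fifty subjects "will be randomized to obtain 40 with complete data (20% projected attrition").

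Section 10, Aim 1, names week-8 ventral striatum to vmPFC FC as the primary endpoint. The time factor of the model is "time (baseline, 8 weeks), and group x time interactions". Week-4 scans go to a separate exploratory analysis. HAM-D-17 is the exploratory Aim 3 outcome and is neither a predictor nor a listed covariate for FC. The plan states no analysis set, estimand, missing-data method or sensitivity analysis.

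The later Stopping Rules paragraph in section 13 words the missed-dose criterion differently: "missing more than 2 doses of medication more than once during the study".

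**The concern.** Two of the removal triggers, depressive worsening and poor adherence, arise after randomisation and may be influenced by the assigned drug. Worsening is a clinical outcome. Missed doses are not, but they may reflect tolerability. If removal also ends scanning, the week-8 FC contrast rests on patients who did not reach these triggers.

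The planned mixed model does not repair this. With two time points, a patient who has only a baseline value carries almost no information on change. Missing-at-random would have to hold without conditioning on HAM-D-17, the variable known to cause part of the missingness. The 20% attrition allowance protects the sample size only.

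The introduction gives a reason to expect unequal loss: it reports poor escitalopram response when CRP is raised. Bupropion intolerance could push the other way.

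**Working it through.** **1. The plan's own figure (section 11).** Expected FC change is 0.20 (SD 0.16) on bupropion and 0.07 (SD 0.10) on escitalopram.
- Pooled SD = √((0.16² + 0.10²)/2) = 0.1334; d = 0.13/0.1334 = 0.974. The plan states 0.97.
- Two-sided t-test, alpha 0.05: 18 per group gives power 0.807 and 20 per group 0.848. The plan's 36 in total reproduces.
- Attrition: 40/(1 − 0.20) = 50.

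**2. Who is lost.** Table 1 appears to schedule HAM-D-17 after baseline at weeks 2, 4 and 8. At week 8 the scan belongs to the same visit, so the HAM-D-17 trigger can cost a week-8 scan mainly at weeks 2 and 4.

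**3. Shift from losing the worst fraction f of one arm.** Let r be the correlation between clinical course and FC change. The mean FC change of those retained rises by r × SD × φ(z_f)/(1 − f). For f = 0.20, φ(z)/(1 − f) = 0.350; for f = 0.10 it is 0.195. The documents give neither f by arm nor r for HAM-D-17. Assumed range: r = 0.2 to 0.43, the upper value being the FC–EEfRT correlation in section 11.

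Loss of 20% from escitalopram only, SD 0.10:
- r = 0.2: 0.350 × 0.2 × 0.10 = 0.0070, which is 5.4% of 0.13.
- r = 0.43: 0.350 × 0.43 × 0.10 = 0.0150, which is 11.6%.
- In units of d: 0.0070/0.1334 = 0.05 and 0.0150/0.1334 = 0.11, so d falls from 0.97 to 0.92 and 0.86.
- Power at 25 versus 20: 0.85 and 0.80.

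The same loss with the pooled SD:
- The shift is 0.350 × r = 0.07 to 0.15 SD, so d = 0.90 to 0.82 and power at 25 versus 20 is 0.83 to 0.76.

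Loss of 10% from escitalopram only, SD 0.10:
- 0.195 × r × 0.10/0.13 = 3% to 6% of the difference.

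Loss of 20% from bupropion only, SD 0.16:
- 0.350 × r × 0.16 = 0.0112 to 0.0241, so the contrast is inflated by about 9% to 19%.

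Equal 20% loss in both arms:
- No shift if the SDs are equal.
- With the plan's SDs, 0.350 × r × (0.16 − 0.10) = 0.0042 to 0.0090, an inflation of about 3% to 7%.

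**4. The discontinuation lists side by side.**
- Section 5, and section 13 for the treatment period: stated without discretion; missed doses must be consecutive; psychotic or catatonic symptoms.
- Section 13, Stopping Rules: at the PI's discretion; the word consecutive is absent; manic/hypomanic symptoms are added.

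These cannot all govern the same decision.

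**The case against.** No sentence says outright that scans stop. That is inferred from the heading, the early-termination wording and the absence of any later assessment. One of the lists leaves discontinuation to the PI's discretion, so removal may not be automatic. The 20% is projected all-cause attrition over both arms; placing all of it in one arm, as exactly the worst patients, is an extreme case. These points stand, and they limit the size of the concern.

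This is also a mechanistic pilot, for which an on-drug contrast is a defensible target. Scanning everyone has its own price. With all 50 scanned (25 per arm), if 20% of bupropion patients showed only the escitalopram mean, the difference would be 0.13 × 0.8 = 0.104, d = 0.78 and power 0.77. This stands as a reason to report both results rather than only the all-randomised one.

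Four stronger readings are tempting but unsupported:
- *Aims 2 and 3 also become comparisons of patients who did not worsen.* Their outcomes are measured repeatedly, and the mixed models keep scores up to discontinuation. They are less affected.
- *Removed patients leave safety observation.* Section 13 provides immediate evaluation by a study psychiatrist, a level-of-care decision and referral. What they leave is the schedule of study assessments.
- *Power falls to about 0.71.* That pairs loss from one arm with 20 per arm. If only one arm loses 20% of 25, the sizes are 25 and 20.
- *The contrast must be understated.* The direction depends on which arm loses more, and the documents do not say.

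**Conclusion.** The concern holds for the primary comparison. As written, patients removed for worsening or repeated missed doses drop out of the week-8 FC contrast for reasons that may relate to the assigned drug, and the two-point model without HAM-D-17 cannot correct for this. The effect is probably modest: under the assumed inputs, 5% to 12% of the planned difference if escitalopram loses its worst 20%, with power still about 0.80 or above, or 0.76 to 0.83 with the pooled SD. It reverses to inflation if bupropion loses more. All of this rests on assumed loss fractions and an assumed link between clinical course and FC. It should be changed because the remedy is cheap, not because the trial fails without it.

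**What to change.** Leave the clinical triggers, and decisions about study drug, as they are. For data collection and analysis:

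1. Separate stopping study drug from leaving the study. Invite these patients to the remaining scheduled assessments and the week-8 scan where the study psychiatrist judges it suitable, or otherwise to one termination assessment.
2. Include week-4 FC as a time point in the primary MMRM, with week 8 still the primary contrast, so that all randomised patients with any post-baseline FC contribute. This does not help a patient stopped at week 2 who has no later scan, which is why step 1 is needed too.
3. Use HAM-D-17 in the missing-data model.
4. State the analysis set, and report both the all-randomised and the on-drug results.
5. Reconcile the lists in sections 5 and 13 on consecutive doses, PI discretion and manic/hypomanic symptoms. Which version is right is for the sponsor and investigators to decide.

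Cost: protocol and consent wording, plus the remaining visits and scans of about 10 patients (50 − 40) at the projected attrition, already scheduled for all 50. Week-4 FC needs no new data. Downside: some week-8 scans will be off drug and dilute the mechanistic contrast; the on-drug analysis addresses this.

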depressed patients with increased inflammation may have unique responsiveness to drugs that target DA. Indeed, preclinical and clinical studies demonstrate that chronic administration of inflammatory stimuli leads to decreased DA availability in ventral striatum (VS) in association with decreased VS activation to rewarding stimuli. In addition, higher inflammation as reflected by CRP is directly linked to lower FC between the DA-rich VS and the ventromedial prefrontal cortex (vmPFC) in MD patients using resting state fMRI. These inflammation-related decreases in VS-vmPFC FC in depressed patients in turn were associated with motivational deficits consistent with an impact of inflammation on RDoC positive valence constructs. Our preliminary data also indicate that administration of the DA-ergic drug L-DOPA increases VS-vmPFC FC (and effort-based motivation) in MD patients with high (CRP>2mg/L) but not low (CRP≤2mg/L) inflammation, using a longitudinal pre- post- neuroimaging design. These data suggest that this circuit and the related behaviors may be especially responsive to DA'ergic medications. Thus, the relationship between CRP and resting state FC within classic reward circuitry in MD patients provides a unique opportunity whereby a functional target in the brain can be used to establish whether there exists differential responsiveness to currently available antidepressants that can be revealed by an inflammatory biomarker (CRP) that is regularly used in clinical practice. Accordingly, this proposal will employ a match/mismatch design, wherein patients with MD and increased inflammation (CRP>2mg/L) and anhedonia will be randomized to bupropion (match) or escitalopram (mismatch). A cut-off of CRP>2mg/L will be used because it predicted increased FC in response to L-DOPA and serves as an excellent translational proxy for a composite of inflammatory mediators in periphery and brain. CRP>2mg/L has also been used in the cardiovascular literature as a threshold for treatment of inflammation. Increased anhedonia will be defined as a score of 2 or greater on item 1 of the PHQ-9.. To examine FC in rewardrelated circuitry, fMRI will be conducted at baseline and after 4 and 8 weeks of treatment. We hypothesize that bupropion (vs escitalopram) will increase FC within reward circuitry in association with improved objective and clinical measures of motivation in patients with high inflammation and anhedonia at baseline. To test this hypothesis, these aims are proposed:

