
Specific Aim 1. To determine whether bupropion (vs escitalopram) will increase functional connectivity in reward circuitry in MD patients with high inflammation and anhedonia. Fifty patients (n=50) with a CRP >2mg/L and an anhedonia score ≥ 2 on item #1 of the PHQ-9 will be stratified by sex and randomized to 8 weeks of bupropion XL up to 300mg/d or escitalopram up to 20 mg/d (as tolerated). FC between VS-vmPFC will be examined at baseline and after 4 and 8 weeks using resting state and task-based fMRI. Hypothesis 1: Bupropion vs escitalopram will increase VS-vmPFC FC in MD patients with high CRP and anhedonia

Specific Aim 2. To determine whether bupropion (vs escitalopram) will improve motivational deficits in MD patients with high inflammation and anhedonia. Objective and clinical measures of RDoC positive valence (motivational) constructs will be assessed in the subjects in Aim 1 at baseline and after 2, 4, 6 and 8 weeks of treatment with bupropion or escitalopram by the Effort-Expenditure for Rewards Task (EEfRT) and the clinician-administered Snaith Hamilton Pleasure Scale and self-report Mood and Pleasure Scale. Hypothesis 2a: Bupropion vs escitalopram will increase the probability of making high effort choices on the EEfRT and improve scores on clinical and self-reported assessments of motivation. Hypothesis 2b: Improvement in VS-vmPFC connectivity will correlate with increased high effort choices on the EEfRT and improved scores on clinical and self-reported assessments of motivation.

Specific Aim 3 (Exploratory). To determine whether bupropion (vs escitalopram) will improve overall depressive symptoms in MD patients with high inflammation and anhedonia. Depressive symptom severity will be assessed by the Hamilton Depression Rating Scale-17 (HAM-D-17) at baseline and after weeks 2, 4, 6 and 8 of treatment in subjects noted in Aim 1. Hypothesis 3: Bupropion vs escitalopram will improve depression severity in MD patients with high CRP and anhedonia at baseline.

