Resting fMRI BOLD: Resting bold will be acquired before and after treatment using phase-encoding directions of opposite polarity (anterior-posterior) for distortion correction. Sequences will be optimized for signal-to-noise ratio and sensitivity to head motion, and collected over ~15 minutes.⁴⁷ Data will be analyzed with standard preprocessing protocols in AFNI (http://afni.nimh.nih.gov/) and SPM12 (www.fil.ion.ucl.ac.uk/spm12/), including slice-timing correction, realignment/motion-correction, anat-to-epi co-registration, and 5mm spatial smoothing. 25, 48, 49 Resting BOLD analysis will also include nuisance signal regression (head motion, cerebral spinal fluid, and white matter) and band pass filtering (0.009Hz<f<0.08Hz). Individual's fMRI data will be normalized into a standard stereotaxic space, MNI template with 1mm3 resolution. *MIDT*: MIDT will be used to assess FC⁵⁰⁻⁵² during reward anticipation. This widely-used task for assessing reward function in psychiatric patients⁵³⁻⁵⁵ is one of the few imaging reward tasks with established test-retest reliability.⁵⁶ Monetary outcome depended on patient performance in a simple reaction time task by pressing a button in response to a visual target stimulus. The "anticipatory delay," ~4000 m, occurs after presentation of a pseudo-randomly distributed cue to inform participants whether a given trial will allow them to win or lose money (reward: +\$; loss: -\$; no incentive: 0\$; averaging ~\$2) but prior to the target stimulus, has reliably been shown to robustly activate ventral striatum.^{53, 57, 58} Participants will complete 2 functional runs of 70 trials each (140 trials total) over ~20 minutes. 50, 52 FC during each anticipation condition will be assessed using beta-series correlation 59 shown to be both powerful and sensitive for assessing task-modulated connectivity^{60, 61} and has been used with MIDT.50,52 Task-based fMRI - Faces Task: This is a task that has been developed to measure brain activity in response to viewing of fearful and neutral faces. For the duration of the task, patients will be instructed to passively view faces as they appear on the screen. The task lasts 5 minutes and proceeds as follows: 15 blocks of 16 trial face stimuli are presented in pseudorandom order. Each block contains 8 fearful faces and 8 neutral faces presented in random order. Each face stimulus is presented for 500ms, followed by a 500ms presentation of a fixation cross. After every 10th block, a 10,000ms rest period is presented. The task has been designed to minimize patient discomfort and enhance cooperation. If at any time a patient experiences negative or unpleasant reaction, they will be removed from the scanner. The addition of these tests does not add to the overall risk to patient safety. DTI: At the first visit, a cmrr mbep2d bold protocol over ~12 minutes will be used calculated fractional anisotropy (FA) maps for each voxel using 3DSlicer.

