
Targeted FC will serve as the primary outcome and will be calculated as the degree of correlation in activity between a 3mm3 radius sphere in VS (see Fig. 1A)^{25, 62} and the vmPFC cluster identified as being reward-sensitive in neuroimaging meta-analyses⁶³ and as used to define vmPFC in our previous work (MNI coordinates x=0, y=44, z=-8, cluster size=1408 mm3 and encompassing parts of BA11 and ventral BA32 of ACC). 25, 62, 64 This method will ensure rigor and reproducibility and application of results to potential future trials because the seeds and ROI cluster are predefined as opposed to those derived from whole-brain and data-driven analyses which are determined based on the specific patient sample. Zscores will be extracted and the change in mean FC values compared to baseline will be calculated. FC between bilateral VS seeds and the vmPFC ROI will be examined separately and treatment-driven change in FC in either the right or left VS will be considered in the analysis. However, based on our previous work in MD and IFN-alpha-induced depression ^{13, 25} and preliminary studies above, we anticipate that changes in FC will be more pronounced on the left side. Additional Analyses for Publication and Dissemination: In addition to the targeted FC that will serve as the primary outcome, hypothesis-driven and data-driven whole-brain analysis will also be explored and compared before and after L-DOPA and placebo. Consistent with our previously published data,65 these analyses will include VS seed-to-voxelwise comparisons of bupropion versus escitalopram, as well as network analyses using GBC and PBNA, as a secondary outcome measure and to identify other circuits that may be differentially affected by the two treatments. For all analyses, concentration of CRP and final dose will be explored as linear predictors of response.

Assessments of Positive Valence (Motivational) Constructs

Objective: Effort-Expenditure for Rewards Task (EEfRT): The EEfRT task is a multi-trial game in which participants are given an opportunity to choose different task difficulty levels to obtain monetary rewards. The task is 20 min, and first 50 trials are analyzed. The proportion of hard-task choices across each level of probability is calculated. Lower proportions of hard task choices indicate decreased motivation.

PI: [name] Sponsor: NIMH

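### The primary outcome takes left and right VS-vmPFC connectivity separately, but no side, modality or success rule is named for Hypothesis 1 and no adjustment is made for two sides

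*Combined protocol and SAP*

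**What the plan says.** **The outcome.** Section 5 (paragraph on targeted FC) defines the primary outcome as the correlation between a predefined VS seed and a predefined vmPFC cluster. It then says "FC between bilateral VS seeds and the vmPFC ROI will be examined separately" and that "treatment-driven change in FC in either the right or left VS will be considered in the analysis". It adds an expectation: "we anticipate that changes in FC will be more pronounced on the left side".

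**The endpoint and model.** Section 10, Aim 1, states "Primary Endpoint: Targeted VS-vmPFC FC at 8 weeks" and the directional hypothesis that "Bupropion vs escitalopram will increase VS-vmPFC FC in depressed patients with high CRP and anhedonia at baseline". It describes one mixed model with group, time and their interaction. It does not say which seed enters the model, whether the two are averaged, or what result supports the hypothesis.

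**Modality.** Section 4, Specific Aim 1, says "FC between VS-vmPFC will be examined at baseline and after 4 and 8 weeks using resting state and task-based fMRI". Section 5 describes a resting-state acquisition and also a monetary incentive task (MIDT), for which "FC during each anticipation condition will be assessed using beta-series correlation". Neither is called primary. The background in Section 4 rests on resting-state evidence, namely "lower FC between the DA-rich VS and the ventromedial prefrontal cortex (vmPFC) in MD patients using resting state fMRI".

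**Multiplicity.** The only family-wise correction in Section 10 is under Hypothesis 2b, directly after the sentence on separate analyses of the behavioural outcomes.

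**Power.** Section 11 uses one between-group comparison with d = 0.97, alpha 0.05 and power above 0.8: 36 patients, with 40 planned for analysis.

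**Interim.** Section 10 breaks the blind after 16 completers and acts on Cohen's d for VS-vmPFC FC, again with no side or modality. If d is below 0.3 at both weeks 4 and 8, the study stops. If d is 0.3 to 0.6 at either week, it continues with its focus on whichever scan showed the larger effect. If d exceeds 0.6, use of the data as proof of concept is discussed with the sponsor.

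**The concern.** Two separate tests of the primary outcome, each at the full alpha and with no rule for combining them, allow more false positives than the single test that was powered. The seeds and cluster are fixed in advance, which prevents data-driven choice of regions. That does not settle which of the two seeds decides Hypothesis 1.

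Three things are at stake: the error rate of the primary claim, the meaning of the stated power (which applies to one pre-named test), and the interim decision. Left and right, or resting and task, could fall on different sides of the 0.3 and 0.6 thresholds. A choice of side made after that look would no longer be independent of the data.

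The time point is less settled than the endpoint line suggests. Section 10 names week 8, yet its interim rule can move the focus to week 4.

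**Working it through.** **1. Reproduce the plan's figure.** Inputs from Section 11: change in FC 0.20 (SD 0.16) after L-DOPA and 0.07 (SD 0.10) after placebo.

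- Pooled SD = sqrt((0.16² + 0.10²)/2) = sqrt(0.0178) = 0.1334.
- d = (0.20 − 0.07)/0.1334 = 0.13/0.1334 = 0.974. The plan says 0.97.
- Non-central t, two-sided 0.05, d = 0.97: power 0.783 with 17 per arm, 0.807 with 18 and 0.848 with 20. The plan's 18 per arm (36 in total) is reproduced.
- A one-sided 0.05 test would need only about 14 per arm. The plan does not state sidedness; two-sided is inferred because it gives N = 36. A false result favouring bupropion on one named test therefore has probability 0.05/2 = 2.5%.

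**2. Error if either side counts.** Let Z_L and Z_R be the test statistics with no true effect and correlation r between sides. The documents give no r, so a range is assumed.

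- Favouring bupropion: 1 − P(Z_L ≤ 1.96 and Z_R ≤ 1.96).
- Either direction: 1 − P(|Z_L| ≤ 1.96 and |Z_R| ≤ 1.96).
- Check at r = 0: 1 − 0.975² = 4.94% and 1 − 0.95² = 9.75%.

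| r (assumed) | Favouring bupropion (one named test: 2.5%) | Either direction (one named test: 5%) |
|---|---|---|
| 0 | 4.94% | 9.75% |
| 0.3 | 4.76% | 9.51% |
| 0.5 | 4.54% | 9.07% |
| 0.8 | 3.90% | 7.81% |
| 0.9 | 3.52% | 7.04% |
| 0.95 | 3.23% | 6.46% |

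Simulated t-tests with 20 per arm (400,000 trials per value of r) agree: 4.9%, 4.5%, 3.9% and 3.5% favouring bupropion at r = 0, 0.5, 0.8 and 0.9, and 9.8%, 9.0%, 7.8% and 7.1% in either direction.

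**3. If task FC could also count.** Two sides by two modalities give four tests. Under independence the rate favouring bupropion is 1 − 0.975⁴ = 9.6%. With assumed correlations of 0.8 between sides and 0.5 between modalities it is about 7.0%.

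**4. Effect of the remedies (20 per arm, left d = 0.97).**

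- One named measure: 2.5% favouring bupropion, power 0.848.
- Hochberg over two sides (both significant if the larger p ≤ 0.05; otherwise the smaller must be ≤ 0.025), with no true effect: 2.1-2.5% favouring bupropion and 4.2-5.0% in either direction for r = 0.9 to 0.
- Power of Hochberg, counting at least one success favouring bupropion, for r = 0.9 to 0.3: 0.84-0.92 if the right side also has d = 0.97; 0.77-0.80 if right d = 0.5; about 0.77 if right d = 0. The last is close to a single test at two-sided 0.025, which has power 0.765.

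These are plain t-tests. They isolate the choice of side and do not simulate the planned mixed model with covariate and model selection.

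**The case against.** The strongest reply is that the plan never says either side alone would establish Hypothesis 1. Considering change on either side is compatible with reporting both descriptively or modelling them jointly, and Section 10 describes a single model. That stands: a reader might infer that an either-side success rule is built into the plan, but the documents support only the absence of a rule. The error rates are therefore conditional.

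Second, the upper end of the range needs r near 0. Both measures use the same vmPFC cluster in the same patients and scans, so a positive correlation is likely. At r = 0.8 to 0.9 the directional rate is 3.5-3.9%, and it is lower above 0.9. This also stands. A reader might say the error doubles; nothing in the documents supports that as the expected size.

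Third, every directional two-side rate above stays below 5%. That is true, but the plan's N implies a two-sided test, for which the either-direction rate exceeds the stated 0.05.

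Fourth, the left-side expectation might be taken to make the left primary. It is worded as an anticipation and follows the sentence that admits either side, so it designates nothing. Section 5 also points to Fig. 1A, which was not available for this check and may mark a side. The family-wise sentence under Hypothesis 2b might be read as general, but its position ties it to the behavioural outcomes.

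Finally, this is a pilot with predefined regions. That limits the consequences, but the plan still states a primary hypothesis, an alpha and a power.

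**Conclusion.** The point holds as a gap in the primary analysis: two seeds are examined separately, and side, modality, success rule and adjustment are all unstated. That much rests on the text alone.

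The inflation is conditional on a significant result on either side counting, on two-sided 0.05, and on an assumed left-right correlation of 0.9 to 0. It would be larger if task FC could also count.

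Two stronger readings are not supported. The documents do not make task FC a separate route to success; its role is merely unclear. Nor is the study shown to be underpowered. The stated power is correct for one pre-named test, and a shortfall to about 0.77 arises only if an adjustment over two sides is applied and the right side has no effect. The plan expects a larger change on the left, which does not mean none on the right.

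This should be fixed, and the timing matters because the interim analysis unblinds FC.

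**What to change.** Before any unblinded look at FC:

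- **Name one measure in Section 10.** For example: the primary endpoint is change from baseline to week 8 in resting-state left VS-vmPFC FC, bupropion versus escitalopram, two-sided 0.05; Hypothesis 1 is supported only if this is significant in favour of bupropion; right-side and MIDT FC are secondary. This follows the plan's own left-side expectation and resting-state evidence. Align the targeted-FC paragraph in Section 5.
- **Use the same measure for the interim effect size.**
- **Reconcile the time point with the interim rule.** Either week 8 remains the confirmatory endpoint whatever the interim shows, or a result at a time point selected at the interim is labelled exploratory.

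If both sides stay primary, or FC has already been unblinded, still name resting state as the single modality, apply Hochberg across the two sides, and restate power with its right-side assumption: 0.84-0.92 if both sides have d = 0.97, about 0.77 if only the left does.

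The cost is a few sentences in Sections 5 and 10 and no new data. The drawback is that an effect seen only on the right or only in the task becomes secondary. Naming one side does not by itself control error from the planned covariate and model selection.
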